Attachment 6: Criteria for Response

The following sections provide a summary of response criteria. Please refer to published international guidelines for the most recent and complete details.

Attachment 6.1: International Workshop on Chronic Lymphocytic Leukemia (IWCLL)

The International Workshop on Chronic Lymphocytic Leukemia (IWCLL) recommendations for the management of CLL in clinical studies and general practice are presented below (Hallek 2008)²³.

| Response Category | Definition |
|---------------------------------|--|
| Complete Response (CR) | 
Group A^{1,2}
 
 • Lymphadenopathy^a: none >1.5cm • Hepatomegaly: none • Splenomegaly: none • Blood lymphocytes: <4000/μL • Marrow^c: Normocellular, <30% lymphocytes, no B-lymphoid nodules. Hypocellular marrow defines CRi 
Group B^{1,2}
 
 • Platelet count: >100,000/μL • Hemoglobin>11 g/dL • Neutrophils^c: >1500/μL 
Complete Response with an Incomplete Marrow Recovery (CRi) is defined as a complete response with an incomplete recovery of the subject's bone marrow. Subjects who have a CRi fulfill the criteria for a CR, but continue to have persistent anemia, thrombocytopenia, or neutropenia, and a hypocellular bone marrow. These cytopenias are due to drug toxicity in the bone marrow and are not due to any evidence of CLL.
 |
| Partial Response (PR) | 
Group A^{1,3}
 
 • Lymphadenopathy^a: Decrease \geq50% • Hepatomegaly: Decrease \geq50% • Splenomegaly: Decrease \geq50% • Blood lymphocytes: Decrease \geq50% from baseline • Marrow^c: 50% reduction in marrow infiltrates or B lymphoid nodules 
Group B^{1,3}
 
 • Platelet count: >100,000/μL or increase \geq50% over baseline • Hemoglobin: >11g/dL or increase \geq50% over baseline • Neutrophils^c: >1500/μL or increase \geq50% over baseline 
Nodular Partial Response (nPR) nPR is a response where subjects meet the criteria for a CR, but the bone marrow biopsy shows that there are still B-lymphoid nodules present. These nodules are residual disease and therefore the subject is termed an nPR.
 
Partial Response (PR) with Lymphocytosis PR with lymphocytosis is a response where subjects meet the criteria for a PR and have persistent lymphocytosis.
 |
| Stable Disease (SD) | Not meeting criteria for CR, CRi, nPR, PR, or PD |
| Progressive Disease (PD) | 
Group A^{1,4}
 
 • Lymphadenopathy^a: increase \geq50% or appearance of new lesions >1.5 cm |

| Response Category | Definition |
|-------------------|--|
| | 
 • Hepatomegaly: increase $\geq 50\%$ or appearance of new hepatomegaly • Splenomegaly: increase $\geq 50\%$ or appearance of new splenomegaly • Blood lymphocytes • Marrow^c: increase $\geq 50\%$ over baseline^d 
Group B^{1, 4}
 
 • Platelet count: Decrease of $\geq 50\%$ from baseline secondary to CLL • Hemoglobin: Decrease of $> 2\text{g/dL}$ from baseline secondary to CLL • Neutrophils^c |
| Other | 
Treatment-related Lymphocytosis
 
Treatment-related lymphocytosis is defined as an elevation in blood lymphocyte count of $\geq 50\%$ compared with baseline that occurs in the setting of unequivocal improvement in at least 1 other disease-related parameter, including lymph node size, spleen size, hematologic parameters (hemoglobin and platelet count), or disease-related symptoms. Treatment-related lymphocytosis is isolated lymphocytosis occurring when no other criteria for progressive disease are met. In this particular setting, it will not be considered PD.
 |

^a. Sum of the products of multiple lymph nodes (as evaluated by CT scans).

^b. Defined as a decrease in lymph nodes of $\geq 50\%$ either in the sum products of the diameter of up to 6 lymph nodes, or in the largest diameter of the enlarged lymph node detected prior to the therapy, as well as no increase in any lymph node and no new enlarged lymph nodes. Note: in small lymph nodes $< 2\text{ cm}$, an increase of $< 25\%$ is not considered to be significant.

^c. This parameter is not relevant for the PD category.

^d. Subjects with treatment-related lymphocytosis should remain on study treatment in the absence of other criteria for progressive disease.

¹. Group A defines the tumor load and Group B defines the function of the hematopoietic system

². CR: all of the criteria need to be met and patients have to lack disease-related constitutional symptoms. Bone marrow aspirate at least 2 months following the last dose of nivolumab is required to confirm CR.

³. PR: At least 2 criteria from Group A plus 1 of the criteria from Group B must be met. In all cases, in order for a response to be termed a PR, the blood lymphocyte count should be normalized or decreased $> 50\%$ from baseline (if elevated at baseline).

⁴. PD: at least 1 of the above criteria from Group A or B are met; or transformation to more aggressive histology (eg, Richter's transformation). A new organ infiltrate, bone lesion, ascites, or pleural effusion confirmed due to CLL would also be considered PD.

Attachment 6.2: Evaluation, Staging, and Response Assessment for Non-Hodgkin Lymphoma: The Lugano Classification (according to Cheson 2014)

Evaluation, staging, and response criteria are summarized in 3 tables below.

Criteria for Involvement of Site

| Tissue Site | Clinical | FDG Avidity | Test | Positive Finding |
|---|-----------------|----------------------|------------------------------|---|
| Lymph nodes | Palpable | FDG-avid histologies | PET-CT | Increased FDG uptake |
| | | Non avid disease | CT | Unexplained node enlargement |
| Spleen | Palpable | FDG-avid histologies | PET-CT | Diffuse uptake, solitary mass, miliary lesions, nodules |
| | | Non avid disease | CT | > 13 cm in vertical length, mass, nodules |
| Liver | Palpable | FDG-avid histologies | PET-CT | Diffuse uptake, mass |
| | | Non avid disease | CT | Nodules |
| CNS | Signs, symptoms | | CT | Mass lesion(s) |
| | | | MRI | Leptomeningeal infiltration, mass lesions |
| | | | CSF assessment | Cytology, flow cytometry |
| Other (eg, skin, lung, GI tract, bone, bone marrow) | Site dependent | | PET-CT ^a , biopsy | Lymphoma involvement |

Abbreviations: CSF, cerebrospinal fluid; CT, computed tomography; FDG, fluorodeoxyglucose; MRI, magnetic resonance imaging; PET, positron emission tomography.

a: PET-CT is adequate for determination of bone marrow involvement and can be considered highly suggestive for involvement of other extralymphatic sites. Biopsy confirmation of those sites can be considered if necessary.

Staging System for Primary Nodal Lymphomas

| Stage | Involvement | Extranodal (E) Status |
|-----------------------|---|--|
| Limited | | |
| I | One node or a group of adjacent nodes | Single extranodal lesions without nodal involvement |
| II | Two or more nodal groups on the same side of the diaphragm | Stage I or II by nodal extent with limited contiguous extranodal involvement |
| II bulky ^a | II as above with “bulky” disease | Not applicable |
| Advanced | | |
| III | Nodes on both sides of the diaphragm; nodes above the diaphragm with spleen involvement | Not applicable |
| IV | Additional noncontiguous extralymphatic involvement | Not applicable |

NOTE. Extent of disease is determined by positron emission tomography–computed tomography for avid lymphomas and computed tomography for nonavid histologies. Tonsils, Waldeyer's ring, and spleen are considered nodal tissue.

a: Whether stage II bulky disease is treated as limited or advanced disease may be determined by histology and a number of prognostic factors.

Criteria for Response Assessment of Non-Hodgkin's Lymphoma

| Response | Site | PET-CT-Based Response | CT-Based Response |
|-----------------|--------------------------------------|--|---|
| Complete | Lymph nodes and extralymphatic sites | Complete metabolic response | Complete radiologic response (all of the following) |
| | | Score 1, 2, or 3 ^a with or without a residual mass on 5PS ² It is recognized that in Waldeyer's ring or extranodal sites with high physiologic uptake or with activation within spleen or marrow (eg, with chemotherapy or myeloid colony-stimulating factors), uptake may be greater than normal mediastinum and/or liver. In this circumstance, complete metabolic response may be inferred if uptake at sites of initial involvement is no greater than surrounding normal tissue even if the tissue has high physiologic uptake | Target nodes/nodal masses must regress to ≤ 1.5 cm in LDi No extralymphatic sites of disease |
| | Non measured lesion | Not applicable | Absent |
| | Organ enlargement | Not applicable | Regress to normal |
| | Bone marrow | No evidence of FDG-avid disease in marrow | Normal by morphology; if determinate, IHC negative |
| Partial | Lymph nodes and extralymphatic sites | Partial metabolic response | Partial remission (all of the following) |
| | | Score 4 or 5 ^b with reduced uptake compared with baseline and residual mass(es) of any size At interim, these findings suggest responding disease At end of treatment, these findings indicate residual disease | $\geq 50\%$ decrease in SPD of up to 6 target measurable nodes and extranodal sites When a lesion is too small to measure on CT, assign 5 mm \times 5 mm as the default value When no longer visible, 0 \times 0 mm For a node > 5 mm \times 5 mm, but smaller than normal, use actual measurement for calculation |
| | Nonmeasured lesion | Not applicable | Absent/normal, regressed, but no increase |
| | Organ enlargement | Not applicable | Spleen must have regressed by $> 50\%$ in length beyond normal |
| | Bone marrow | Residual uptake higher than uptake in normal marrow but reduced compared with baseline (diffuse uptake compatible with reactive changes from chemotherapy allowed). If there are persistent focal changes in the marrow in the context of a nodal response, consideration should be given to further evaluation with MRI or biopsy or an interval scan | Not applicable |

| Response | Site | PET-CT-Based Response | CT-Based Response |
|--------------------------------------|--|--|--|
| No response or stable disease | Lymph nodes and extralymphatic sites | No metabolic response | Stable disease |
| | | Score 4 or 5 with no significant change in FDG uptake from baseline at interim or end of treatment | < 50% decrease from baseline in SPD of up to 6 dominant, measurable nodes and extranodal sites; no criteria for progressive disease are met |
| | Non measured lesion | Not applicable | No increase consistent with progression |
| | Organ enlargement | Not applicable | No increase consistent with progression |
| | New lesions | None | None |
| | Bone marrow | No change from baseline | Not applicable |
| Progressive disease | Individual target nodes/nodal masses Extranodal lesions | Progressive metabolic disease Score 4 or 5 with an increase in intensity of uptake from baseline and/or New FDG-avid foci consistent with lymphoma at interim or end-of-treatment assessment | Progressive disease requires at least 1 of the following: PPD progression: An individual node/lesion must be abnormal with: LDi > 1.5 cm and Increase by $\geq 50\%$ from PPD nadir and An increase in LDi or SDi from nadir. 0.5 cm for lesions ≤ 2 cm 1.0 cm for lesions > 2 cm In the setting of splenomegaly, the splenic length must increase by $> 50\%$ of the extent of its prior increase beyond baseline (eg, a 15-cm spleen must increase to > 16 cm). If no prior splenomegaly, must increase by at least 2 cm from baseline New or recurrent splenomegaly |
| | Non measured lesions | None | New or clear progression of preexisting nonmeasured lesions |
| | New lesions | New FDG-avid foci consistent with lymphoma rather than another etiology (eg, infection, inflammation). If uncertain regarding etiology of new lesions, biopsy or interval scan may be considered | Regrowth of previously resolved lesions A new node > 1.5 cm in any axis A new extranodal site > 1.0 cm in any axis; if < 1.0 cm in any axis, its presence must be unequivocal and must be attributable to lymphoma Assessable disease of any size unequivocally attributable to lymphoma |
| | Bone marrow | New or recurrent FDG-avid foci | New or recurrent involvement |

Abbreviations: 5PS, 5-point scale; CT, computed tomography; FDG, fluorodeoxyglucose; IHC, immunohistochemistry; LDi, longest transverse diameter of a lesion; MRI, magnetic resonance imaging; PET, positron emission tomography; PPD, cross product of the LDi and perpendicular diameter; SDi, shortest axis perpendicular to the LDi; SPD, sum of the product of the perpendicular diameters for multiple lesions.

- ^a: A score of 3 in many patients indicates a good prognosis with standard treatment, especially if at the time of an interim scan. However, in trials involving PET where de-escalation is investigated, it may be preferable to consider a score of 3 as inadequate response (to avoid undertreatment). Measured dominant lesions: Up to six of the largest dominant nodes, nodal masses, and extranodal lesions selected to be clearly measurable in two diameters. Nodes should preferably be from disparate regions of the body and should include, where applicable, mediastinal and retroperitoneal areas. Non-nodal lesions include those in solid organs (eg, liver, spleen, kidneys, lungs), GI involvement, cutaneous lesions, or those noted on palpation. Nonmeasured lesions: Any disease not selected as measured, dominant disease and truly assessable disease should be considered not measured. These sites include any nodes, nodal masses, and extranodal sites not selected as dominant or measurable or that do not meet the requirements for measurability but are still considered abnormal, as well as truly assessable disease, which is any site of suspected disease that would be difficult to follow quantitatively with measurement, including pleural effusions, ascites, bone lesions, leptomeningeal disease, abdominal masses, and other lesions that cannot be confirmed and followed by imaging. In Waldeyer's ring or in extranodal sites (eg, GI tract, liver, bone marrow), FDG uptake may be greater than in the mediastinum with complete metabolic response, but should be no higher than surrounding normal physiologic uptake (eg, with marrow activation as a result of chemotherapy or myeloid growth factors).
- ^b: PET 5PS: 1, no uptake above background; 2, uptake \leq mediastinum; 3, uptake $>$ mediastinum but \leq liver; 4, uptake moderately $>$ liver; 5, uptake markedly higher than liver and/or new lesions; X, new areas of uptake unlikely to be related to lymphoma.

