| 
Treatment Period begins with the first administration of study therapy. EOT visit is required for all subjects and should take place within 30 days after last dose of study therapy with a window of ± 7 days. If the subject requires subsequent anti-lymphoma/neoplastic therapy in the interim period between last dose of study drug and the EOT visit, then this visit should be completed just prior to initiation of subsequent therapy. Follow-up visits in all subjects will be completed every 3 months with a window of ± 7 days until death or end of study. Note that the first FU visit should be approximately 100 days after end of nivolumab therapy; during this first FU visit, additional sampling will be done.
 
After the clinical cutoff, subjects who are ongoing on treatment continue all assessment per protocol, however data collected on eCRF will be limited to at least: SAEs and AEs Grade ≥ 3, laboratory assessments (Grade ≥ 3 or clinically significant), efficacy assessments, survival status, and study treatment administration.
 
Per Amendment 7, subjects who are receiving study treatment will continue all assessments per protocol. Data collected in the eCRF will be further limited to: SAEs and Grade ≥ 3 AEs that are at least possibly related to treatment, AEs leading to discontinuation or modification, efficacy assessments, and study treatment administration.
 | | | | | | |
| Bone marrow aspirate; biopsy | Morphological examination of the bone marrow is required; bone marrow aspirate/ bone marrow biopsy: at least 1 assessment is mandatory. Extent of disease involvement in the bone marrow must be documented at screening based on the results of a bone marrow biopsy/aspirate performed within 90 days prior to enrollment or a bone marrow biopsy/aspirate performed during the screening period. If bone marrow biopsy/aspirate is performed during screening (after obtaining informed consent), submission of bone marrow aspirate is encouraged. In subjects with bone marrow involvement prior to treatment, bone marrow aspirate or biopsy must be repeated once during the study for confirmation of CR (preferably within 30 days of initial documentation of CR). Assessment will not be conducted post clinical cutoff. | X | | | | to confirm CR |
| Survival ^a | | | | | | X |
| Pharmacokinetic and Pharmacodynamic Assessments | | | | | | |
| Please refer to Table 2 . | | | | | | |
| Biomarker Assessments | | | | | | |
| Please refer to Table 2 . | | | | | | |

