6. DOSAGE AND ADMINISTRATION

6.1. Study Treatment Administration

For the purposes of this study, ‘study drug’ or ‘study therapy’ refers to both ibrutinib and/or nivolumab. All dosing information must be recorded in the Dosage Administration page of the eCRF. A treatment and study design scheme is provided in [Figure 1](#).

The duration of each treatment cycle is 14 days. Day 1 or start day of a new cycle is triggered by the infusion of nivolumab. The cycle duration may be changed based on decision by the SET (Section 3.3). Study drugs will be administered until disease progression or unacceptable toxicity,

whichever occurs first. On days when both drugs will be administered, the sequence of administration will be nivolumab IV followed by oral ibrutinib.

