6.1.2. Dosing Schedule

Study drugs will be administered as described below in Table 5.

Table 5: Ibrutinib and Nivolumab Dosing Schedule

| | Ibrutinib Run-in, Day -7 to Day 1 | Cycle 1 Day 1 | Cycle 2 Day 1 | Day 1 of every cycle, Cycle 3 and all subsequent cycles |
|---------------------------------|--------------------------------------|---------------------------------|---------------|--|
| | | DLT Determinative Period | | |
| Part A, Cohort A1 and A2 | | | | |
| Ibrutinib | | <-----continuous dosing-----> | | |
| Nivolumab ^a | | 3 mg/kg | 3 mg/kg | 3 mg/kg |
| Part B, Cohort B1 and B2 | | | | |
| Ibrutinib | | <-----continuous dosing-----> | | |
| Nivolumab ^a | | 3 mg/kg | 3 mg/kg | 3 mg/kg |
| Part B, Cohort B3 and B4 | | | | |
| Ibrutinib | | <-----continuous dosing-----> | | |
| Nivolumab ^a | | 3 mg/kg | 3 mg/kg | 3 mg/kg |

^a Nivolumab administered first followed by ibrutinib.

Ibrutinib Run-in Period: In Cohort B1 and B2, to assess pharmacokinetic and pharmacodynamic characteristics of ibrutinib monotherapy, ibrutinib will be given at the recommended Phase 2 dose over an initial period of seven days prior to the first dose of nivolumab (Day -7 to -1).

Nivolumab will be administered on Day 1 of each 14-day treatment cycle.

DLT Period: DLT will be documented over the first 2 cycles beginning with the first concomitant administration of ibrutinib and nivolumab on Day 1 of Cycle 1.

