6.3. Nivolumab Administration

Eligible subjects will receive treatment with nivolumab at a dose of 3 mg/kg given as a 60-minute IV infusion on Day 1 of every 14-day cycle. If the subject's weight on the day of dosing differs by > 10% from the weight used to calculate the dose, the dose must be recalculated. All doses should be rounded to the nearest milligram.

There are no premedications recommended for nivolumab on the first cycle. If an acute infusion reaction is noted, subjects should be managed according to guidelines provided in Section 8.11.

Subjects may receive nivolumab infusions with no less than 12 days between doses and no more than 3 days after the scheduled dosing date. A dose given after the 3-day window is considered a dose delay. A maximum delay of 42 days between doses is allowed.

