6.4.3. Guidelines for Dose Modification

Guidelines for dose modifications following occurrence of general toxicities are listed in Table 8. For immune-related adverse events and other events of clinical interest, guidelines for dose modification are listed in Table 9.

Of note: **Guidelines for the management of immune-related adverse events and adverse events of clinical interest** are provided in Section 8.

If the criterion to resume treatment is met, the subject should restart treatment at the next scheduled timepoint per protocol.

If treatment is delayed > 6 weeks, the subject must be permanently discontinued from study therapy, except as specified in the protocol.

Table 8: Dose Adjustments for Related Non-hematologic and Related Hematologic Toxicities

| Adverse Event | CTCAE Grade | Ibrutinib and Nivolumab * |
|---|---|---|
| *For immune-related toxicities please see Table 9. Additional information may also be found in the latest IB sections (appendix on nivolumab adverse event management, algorithm management sections) Recommendations for the management of immune-related adverse events and adverse events of clinical interest are provided in Section 8. | | |
| Non-Hematologic Toxicity [see separate table for Immune-related toxicities and adverse events of clinical interest) | | |
| General | Grade 1 | Continue therapy. |
| | Grade 2 | Persistent ^a ≤12 weeks: Continue study therapy. Persistent ^a >12 weeks: Discontinue study therapy |
| | Grade 3 | 1st event: Hold study therapy until resolution to Grade ≤ 1 
 Persistent^a ≤12 weeks: Resume at same dose Persistent^a >12 weeks: Discontinue study therapy 2nd event: discontinue study therapy |
| | Grade 4 | Discontinue study therapy |
| Fatigue | Grade 1 | Continue study therapy |
| | Grade 2 | Persistent ^a ≤12 weeks: Continue study therapy. Persistent ^a >12 weeks: Discontinue study therapy |
| | Grade 3 | 1st event: Hold study therapy until resolution to Grade ≤ 1 
 Persistent^a ≤12 weeks: Resume at same dose Persistent^a >12 weeks: Discontinue study therapy 2nd event: Discontinue study therapy |
| Alopecia | Grade 1 | Continue study therapy |
| | Grade 2 | Persistent ^a ≤12 weeks: Continue study therapy. Persistent ^a >12 weeks: Discontinue study therapy |
| Hemorrhagic events | Grade 1 | Continue study therapy; contact sponsor. |

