| Thrombocytopenia | Grade 1-3 | Continue study therapy; supportive therapy as per local/institutional guidelines | | |
| | Grade 4 | Hold study therapy until baseline or Grade 1; supportive therapy as per local/institutional guidelines: | | |
| | | Toxicity Occurrence | Starting dose = 560 mg | Starting Dose = 420 mg |
| | | First | Restart at 560 mg | Restart at 420 mg |
| | | Second | Restart at 420 mg | Restart at 280 mg |
| | | Third | Restart at 280 mg | Discontinue study therapy |

- a. Persistent treatment-related adverse event that do not recover to Grade ≤ 1 within 12 weeks after last dose of nivolumab.

Table 9: Dose Adjustments for Immune-related Adverse Events

| | | |
|--|--|---|
| Recommendations for the management of immune-related adverse events and adverse events of clinical interest are provided in Section 8. | | |
| Adverse Event | CTCAE Grade | Ibrutinib and Nivolumab |
| Immune-related AE (irAE) | Section 8: Guidelines for Management of Immune Related Adverse Events | |
| | Grade 1 | Continue study therapy. |
| | Grade 2 | Consider hold study therapy until resolution to Grade ≤ 1 Persistent ^a ≤ 12 weeks: Continue therapy at same dose and schedule. Persistent ^a > 12 weeks: Discontinue study therapy |
| | Grade 3 | 1st event: hold study therapy, resume only after discussion/agreement with sponsor and resolution to Grade ≤ 1 2nd event: discontinue study therapy |
| | Grade 4 | Discontinue study therapy. |
| Recommendations for the management of immune-related adverse events and adverse events of clinical interest are provided in Section 8. | | |
| Adverse Event | CTCAE Grade | Ibrutinib and Nivolumab |
| Infusion Reaction | Section 8.11 (Table 18): Management of Nivolumab Related Infusion Reactions | |
| | Grade 1 | Continue study therapy. |
| | Grade 2 | Hold study therapy until resolution to Grade ≤ 1 1st event: resume at same dose and schedule. 2nd event (despite pre-medication, antihistamines, non-steroidal anti-inflammatory drugs, corticosteroids, bronchodilators, IV fluids; |

Table 8: Dose Adjustments for Related Non-hematologic and Related Hematologic Toxicities

| | | |
|--|---|---|
| | | prophylactic medications indicated for <24 hours]); discontinue study therapy. |
| | Grade 3 and 4 | Discontinue study therapy. |
| Enterocolitis or diarrhea | Section 8.1. (Table 10): Management of Gastrointestinal Adverse Events | |
| | Grade 1 | Continue study therapy. |

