PET using [18F]-fluorodeoxyglucose (FDG) is important for the complete assessment of response and progression in subjects with DLBCL. Whole body FDG-PET scan (skull base to the proximal femur) is recommended at Screening, at the time of maximal tumor reduction (eg, CR or 2 consecutive CT scans showing no further tumor reduction), and relapse from CR. For subjects with PET-negative tumors at baseline, the response evaluation will be based on the CT scan.

Assessment of PET results is based on published criteria.

Visual assessment is considered adequate for determining whether a PET scan is positive, and use of the standardized uptake value is not necessary. A positive scan is defined as focal or diffuse FDG uptake above background in a location incompatible with normal anatomy or physiology, without a specific standardized uptake value cutoff. Other causes of false-positive scans should be ruled out. Exceptions include mild and diffusely increased FDG uptake at the site of moderate- or large-sized masses with an intensity that is lower than or equal to the mediastinal blood pool, hepatic or splenic nodules 1.5 cm with FDG uptake lower than the surrounding liver/spleen uptake, and diffusely increased bone marrow uptake within weeks after treatment.

Bone Marrow Assessment

Bone marrow aspirate is mandatory and biopsy is optional at Screening (see [Table 1](#)). Subjects with bone marrow involvement must have a repeat bone marrow evaluation at the time of CR (preferably within 30 days of the initial documentation of CR). If bone marrow involvement can be confirmed with morphology, IHC or flow cytometry need not be done; 1 bone marrow examination is necessary for complete documentation of the CR.

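### The marrow rule for confirming CR in CLL cannot be met while nivolumab continues, and it conflicts with the marrow timing in Tables 1 and 2 and Attachment 5

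*Protocol*

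**What the plan says.** **The confirmation rule.** Footnote 2 of protocol Attachment 6.1 (the IWCLL criteria) reads: "Bone marrow aspirate at least 2 months following the last dose of nivolumab is required to confirm CR". By protocol Table 21 these criteria apply to CLL subjects in Part A and to the CLL subjects in Cohort B1. SLL subjects, including those in B1, are assessed by the Lugano criteria in Attachment 6.2, which carry no such footnote. SAP section 4.1.3 follows the same split and points to protocol section 10.1 for the criteria.

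**The treatment schedule.** Protocol section 6.1: "Study drugs will be administered until disease progression or unacceptable toxicity". Section 6.1.2: "Nivolumab will be administered on Day 1 of each 14-day treatment cycle". Section 6.3: "A maximum delay of 42 days between doses is allowed". Section 6.4.3: "If treatment is delayed > 6 weeks, the subject must be permanently discontinued from study therapy, except as specified in the protocol".

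**The marrow schedule.** For subjects with marrow involvement before treatment, the bone marrow row of Table 1 says that marrow sampling "must be repeated once during the study for confirmation of CR (preferably within 30 days of initial documentation of CR"). Attachment 5 says that subjects with marrow involvement "must have a repeat bone marrow evaluation at the time of CR", with the same 30-day preference. Table 2 has a marrow entry in its row for CR. None of these mentions time since nivolumab. Table 1 also ends marrow assessment at the clinical cutoff.

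**The concern.** The footnote asks for a drug-free interval that the treatment schedule does not provide. A site that follows Table 1 during treatment takes the one marrow it requires at a time that footnote 2 does not accept. A site that follows footnote 2 cannot confirm a CR while the subject remains on nivolumab. The protocol does not rank the two rules, and the SAP has no rule for a CR that lacks the marrow described in the footnote.

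At stake is the depth of response in CLL. SAP section 2.7 ranks CR first and CRi second, above PR, and dates the best response from the first visit at which it is reported. CRi depends on the same rule, because Attachment 6.1 defines it as meeting the CR criteria apart from persistent cytopenia and a hypocellular marrow. Assessment is by the investigator, so two subjects with the same findings could be given different best responses according to which passage their site followed.

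**Working it through.** **1. The plan's own figure.** Protocol section 12.3 gives a null ORR of 20%, an alternative of 38%, one-sided alpha 0.1, power of at least 0.8, and 32 evaluable of about 35 enrolled per Part B cohort. With an exact binomial test that rejects at 10 or more responses in 32:

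- alpha = P(X ≥ 10 | n = 32, p = 0.20) = 0.0898
- power = P(X ≥ 10 | n = 32, p = 0.38) = 0.833

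At n = 31 the cut-off is also 10 and power is 0.799. The figure of 32 is reproduced and is used again in step 5.

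**2. Two months in days.** SAP section 2.7 sets 1 month = 30.4375 days, so 2 × 30.4375 = 60.875 days.

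**3. Longest interval between nivolumab doses for a subject who continues.**

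| Reading | Source | Days |
|---|---|---|
| Scheduled cycle | 6.1.2 | 14 |
| Cycle plus the 3-day window | 6.3 | 14 + 3 = 17 |
| 42 days as the whole interval | 6.3 | 42 |
| 42 days added to the cycle | 6.3, loose reading | 14 + 42 = 56 |
| 42 days added to cycle and window | 6.3, loosest reading | 14 + 3 + 42 = 59 |

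Every reading is below 60.875 days; the loosest falls short by 60.875 − 59 = 1.875 days. The footnote cannot be met on continuing nivolumab.

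**4. When it can be met.**

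- Nivolumab stops and the subject continues on ibrutinib alone, which section 6.4 allows after consultation with the sponsor.
- The subject stops treatment without progression. Attachment 5 keeps such subjects on scheduled efficacy assessments.
- Possibly, a toxicity hold. The footnotes to Tables 8 and 9 use a window "within 12 weeks after last dose of nivolumab", which is 12 × 7 = 84 days. A hold of about 61 to 84 days would qualify only if that window overrides the 6-week limit (6 × 7 = 42 days) in section 6.4.3. That section has an exception clause but does not say whether it covers this case.

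No marrow is scheduled by time since nivolumab in any of these situations. The Table 2 follow-up row at 100 days after the last nivolumab dose lists only nivolumab PK and anti-drug antibodies. The marrow entries that serve to confirm CR are triggered by the CR.

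**5. What changes and what does not.** Protocol section 10.1 counts CR or PR in ORR; SAP section 4.2.1 counts partial response or better. A CLL subject who meets every CR criterion except the late marrow still meets the PR criteria and stays in the numerator. The 10-of-32 rule, alpha 0.0898 and power 0.833 stand. The CR/CRi count in CLL, the CR/PR split, best response and date of best response do change with the rule applied.

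**6. How many subjects.** This would need the CLL/SLL split of B1, the CLL CR rate, the number who stop nivolumab without progression, and which rule each investigator applied. The documents give none of these.

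**The case against.** The strongest reply is that nothing forces the footnote to be applied. Tables 1 and 2 and Attachment 5 already provide a marrow at CR, Attachment 6 introduces itself as a summary and sends readers to the published guidelines, and response is judged by the investigator. This stands as far as it goes, and it is why the finding is an unreconciled contradiction and not an impossibility throughout the protocol. It does not remove the problem: the footnote makes the late marrow a requirement, and the SAP's reference to protocol section 10.1 leads to it.

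A second reply is that the two rules can coincide. The 30-day timing is a preference, and a subject who stopped nivolumab for toxicity and reached CR later could satisfy both. That is right, but it covers only subjects already off nivolumab.

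A third is that little depends on it. CR rate is not a listed endpoint, the Part B benchmark is a 20% ORR, and best response enters mainly descriptive and biomarker summaries. This stands and limits the weight of the point.

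Three stronger readings are tempting but not supported:

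- *CR in B1 is close to zero by construction.* This would need every investigator to apply the footnote over Table 1. It also ignores the SLL subjects and those who stop nivolumab without progression.
- *Some 3 to 7 of 35 subjects are downgraded to PR.* This comes from 35 × 0.10 = 3.5 and 35 × 0.20 = 7. The 10–20% CR rate is an assumption with no anchor in the documents, and 35 includes SLL subjects.
- *Most CLL responders are still on nivolumab at the cutoff, because the SAP expects a 15-month median.* That median is for study therapy, which may be ibrutinib alone. The cutoff is 6 months after the last subject's first dose (or earlier if that subject stops therapy), so earlier subjects have longer follow-up that depends on accrual.

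**Conclusion.** The point holds for CLL subjects in Part A and the CLL part of B1. Footnote 2 cannot be met while nivolumab continues: the interval required is 60.875 days, against an allowed maximum of 42, or 59 on the loosest reading. It also conflicts with the marrow timing in Tables 1 and 2 and Attachment 5, and no passage says which governs. Applied literally, it understates CLL CR and CRi; applied unevenly, it makes best response and its date inconsistent between sites.

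The timing result rests on the SAP's month length and on the dose-interval limits in protocol sections 6.1.2 and 6.3. A reader might infer that the primary result is biased; it is not, because a CR that is not confirmed still counts as PR in ORR. The number of subjects affected cannot be estimated from the documents.

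**What to change.** Reconcile footnote 2 of Attachment 6.1 with the marrow row of Table 1, the CR row of Table 2 and the bone marrow paragraph of Attachment 5. One marrow-timing rule for CLL CR and CRi should result, and it should be one that a subject treated until progression can meet. The choice of timing is the sponsor's; what matters for the analysis is that there is one rule and that the SAP says how a CR without the required marrow is classified.

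In the report, list every CLL CR and CRi with the date first documented, the marrow date, and the days from the last nivolumab dose to the marrow. A reader can then see which rule each classification satisfies.

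The cost is one footnote (with a matching SAP sentence) and one listing from data already collected, with no added procedures if the existing Table 1 marrow is used. Amendment 7 says the primary and secondary objectives have been analyzed and published, and marrow sampling stopped at the clinical cutoff. Rewording the footnote therefore recovers no data; for results already in hand, the listing is the useful part.
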